9.5.3 EXPLORATORY ENDPOINTS

Patient level exploratory endpoints will be summarized using frequency (in %) if they are dichotomous or categorical and mean (std) if they are numerical respectively. Endpoints will be assessed of relations or associations using regression models, ANOVA models and logistical models respectively to accommodate numerical and categorical types of dependent and independent variables (i.e. endpoints).

9.6 STATISTICAL METHODS

9.6.1 DISEASE FREE SURVIVAL

The distributions of DFS will be summarized using the Kaplan-Meier (KM) curves and the median DFS and its associated 95% CIs will be estimated. The DFSs at 1- and 2-year will be also summarized with its associated 95% CIs. In addition, KM curves will be used to assess DFS and OS of the patients. Median survival time and its associated 95% CI will be estimated from the KM curves.

9.6.2 SAFETY ANALYSIS

Descriptive statistics will be provided for safety endpoints. In particular, the dichotomous primary and secondary endpoints will be summarized using frequency (in %) with a 95% CI calculated using a binomial distribution. The binomial test (or the Exact test) will be used to test the hypothesis proposed in 9.3.

9.6.3 BIOMARKER ASSESSMENTS

All biomarker measures will be summarized with descriptive statistics, i.e., percentages for categorical outcomes and means/medians for continuous outcomes, with corresponding standard errors and 95% confidence intervals. Responses will be tabulated by determined response and toxicities will be tabulated by type and grade. For IHC, the percentage of positive cells per area will be multiplied by the staining intensity for each tumor to determine quantitative expression in pre treatment tissue and post-treatment if available. ; We will use descriptive statistics and graphical displays to evaluate change in plasma markers and flow cytometry markers between pre- and post-treatment.

10.2 COMPLIANCE WITH FINANCIAL DISCLOSURE REQUIREMENTS

Financial Disclosure requirements are outlined in the US Food and Drug Administration Regulations, Financial Disclosure by Clinical Investigators (21 CFR Part 54). It is the Sponsor's responsibility to determine, based on these regulations, whether a request for Financial Disclosure information is required. It is the investigator's/sub-investigator's responsibility to comply with any such request.

10.2.1 COMPLIANCE WITH LAW, AUDIT AND DEBARMENT

By signing this protocol, the investigator agrees to conduct the trial in an efficient and diligent manner and in conformance with this protocol; generally accepted standards of Good Clinical Practice (e.g., International Conference on Harmonization of Technical Requirements for Registration of Pharmaceuticals for Human Use Good Clinical Practice: Consolidated Guideline and other generally accepted standards of good clinical practice); and all applicable federal, state and local laws, rules and regulations relating to the conduct of the clinical trial.

10.2.2 COMPLIANCE WITH TRIAL REGISTRATION AND RESULTS POSTING REQUIREMENT

Under the terms of the Food and Drug Administration Modernization Act (FDAMA) and the Food and Drug Administration Amendments Act (FDAAA), the Sponsor of the trial is solely responsible for determining whether the trial and its results are subject to the requirements for submission to the Clinical Trials Data Bank, <http://www.clinicaltrials.gov>. Information posted will allow subjects to identify potentially appropriate trials for their disease conditions and pursue participation by calling a central contact number for further information on appropriate trial locations and trial site contact information.

10.3 QUALITY MANAGEMENT SYSTEM

By signing this protocol, the Sponsor agrees to be responsible for implementing and maintaining a quality management system with written development procedures and functional area standard operating procedures (SOPs) to ensure that trials are conducted and data are generated, documented, and reported in compliance with the protocol, accepted standards of Good Clinical Practice, and all applicable federal, state, and local laws, rules and regulations relating to the conduct of the clinical trial.

10.4 DATA MANAGEMENT

10.4.1 DATA STORAGE

Data collection and storage will be managed by the University of Cincinnati Cancer Institute, Clinical Trials Office (UCCI CTO). The UCCI CTO will maintain storage of all clinical data in accordance with federal guidelines and GCP. Data will be entered in a secure, password protected storage database, OnCore as well as RedCap. All hardcopies of data will be securely maintained (in a locked room or cabinet) and will only be accessible to members of the study team.

10.4.2 DATA AND SAFETY MONITORING

Adverse event lists, guidelines, and instructions for AE reporting can be found in Section 8.0

Any new significant finding that may affect the patient's willingness to continue in the study will be shared with patients. Each patient, once enrolled, will be provided a unique ID for the study. Confidentiality will be maintained during the phases of the trial including any monitoring, and preparation of interim results. Exceptions may be made under circumstances where there are serious adverse events or when it is deemed appropriate for patient safety.

Study progress will be monitored regularly by the UCCI Data Safety Monitoring Board (DSMB). Membership consists of persons independent of, and without any conflicts of interest with, this trial. The DSMB includes experts in the fields of relevant clinical expertise (oncology) and biostatistics.

It is the responsibility of the sponsor-investigator to ensure that the DSMB is apprised of all new safety information relevant to the study IND and the study. Study progress & safety information will be prepared by the DSMB Coordinator with input from the PI as to the current status of the trial. This compiled information presented to the DSMB will include: a narrative summary from the PI as to trial progress and identification of any trends of significance or explanation of any SAEs or other safety related events; the accrual rate with projected completion date for the accrual phase; exclusion rates and reasons; pretreatment characteristics of patients accrued when relevant; and, the frequency and severity of adverse events.

The DSMB will function in an advisory capacity and recommendations/requests from the DSMB will be reviewed by the sponsor-investigator and promptly addressed.

The study data from any participating sub-sites will be reviewed remotely via RedCAP and in person by the Study Monitor as per the Clinical Monitoring Plan (Plan kept on file with UCCI CTO).

11.0 APPENDICES

Appendix 1. ECOG Performance Status

Grade	Description
0	Normal activity. Fully active, able to carry on all pre-disease performance without restriction.
1	Symptoms, but ambulatory. Restricted in physically strenuous activity, but ambulatory and able to carry out work of a light or sedentary nature (e.g., light housework, office work).
2	In bed <50% of the time. Ambulatory and capable of all self-care, but unable to carry out any work activities. Up and about more than 50% of waking hours.
3	In bed >50% of the time. Capable of only limited self-care, confined to bed or chair more than 50% of waking hours.
4	100% bedridden. Completely disabled. Cannot carry on any self-care. Totally confined to bed or chair.
5	Dead.
* As published in Am. J. Clin. Oncol.: Oken, M.M., Creech, R.H., Tormey, D.C., Horton, J., Davis, T.E., McFadden, E.T., Carbone, P.P.: Toxicity And Response Criteria Of The Eastern Cooperative Oncology Group . Am J Clin Oncol 5:649-655, 1982. The Eastern Cooperative Oncology Group, Robert Comis M.D., Group Chair.	

[figure not shown]
11.1 COMMON TERMINOLOGY CRITERIA FOR ADVERSE EVENTS V5.0 (CTCAE)

THE DESCRIPTIONS AND GRADING SCALES FOUND IN THE REVISED NCI COMMON TERMINOLOGY CRITERIA FOR ADVERSE EVENTS (CTCAE) VERSION 5.0 WILL BE UTILIZED FOR ADVERSE EVENT REPORTING.
([HTTP://CTEP.CANCER.GOV/REPORTING/CTC.HTML](http://CTEP.CANCER.GOV/REPORTING/CTC.HTML))

11.2 APPENDIX 2 IMMUNO-ONCOLOGY ALGORITHMS

GI Adverse Event Management Algorithm

Rule out non-inflammatory causes. If non-inflammatory cause is identified, treat accordingly and continue I-O therapy. Opiates/narcotics may mask symptoms of perforation. Infliximab should not be used in cases of perforation or sepsis.

[figure not shown]

Patients on IV steroids may be switched to an equivalent dose of oral corticosteroids (e.g. prednisone) at start of tapering or earlier, once sustained clinical improvement is observed. Lower bioavailability of oral corticosteroids should be taken into account when switching to the equivalent dose of oral corticosteroids.

Updated 03-Jul-2016

Renal Adverse Event Management Algorithm

Rule out non-inflammatory causes. If non-inflammatory cause, treat accordingly and continue I-O therapy

[figure not shown]

Patients on IV steroids may be switched to an equivalent dose of oral corticosteroids (e.g. prednisone) at start of tapering or earlier, once sustained clinical improvement is observed. Lower bioavailability of oral corticosteroids should be taken into account when switching to the equivalent dose of oral corticosteroids.

Updated 05-Jul-2016

Pulmonary Adverse Event Management Algorithm

Rule out non-inflammatory causes. If non-inflammatory cause, treat accordingly and continue I-O therapy. Evaluate with imaging and pulmonary consultation.

[figure not shown]

Patients on IV steroids may be switched to an equivalent dose of oral corticosteroids (e.g. prednisone) at start of tapering or earlier, once sustained clinical improvement is observed. Lower bioavailability of oral corticosteroids should be taken into account when switching to the equivalent dose of oral corticosteroids.

Updated 05-Jul-2016

Hepatic Adverse Event Management Algorithm

Rule out non-inflammatory causes. If non-inflammatory cause, treat accordingly and continue I-O therapy. Consider imaging for obstruction.

Patients on IV steroids may be switched to an equivalent dose of oral corticosteroids (e.g. prednisone) at start of tapering or earlier, once sustained clinical improvement is observed. Lower bioavailability of oral corticosteroids should be taken into account when switching to the equivalent dose of oral corticosteroids.

[figure not shown]
*I-O therapy may be delayed rather than discontinued if AST/ALT ≤ 8 x ULN or T.bili ≤ 5 x ULN.

**The recommended starting dose for grade 4 hepatitis is 2 mg/kg/day methylprednisolone IV.

Updated 05-Jul-2016

Endocrinopathy Management Algorithm

Rule out non-inflammatory causes. If non-inflammatory cause, treat accordingly and continue I-O therapy. Consider visual field testing, endocrinology consultation, and imaging.

[figure not shown]

Patients on IV steroids may be switched to an equivalent dose of oral corticosteroids (e.g. prednisone) at start of tapering or earlier, once sustained clinical improvement is observed. Lower bioavailability of oral corticosteroids should be taken into account when switching to the equivalent dose of oral corticosteroids.

Updated 05-Jul-2016

Skin Adverse Event Management Algorithm

Rule out non-inflammatory causes. If non-inflammatory cause, treat accordingly and continue I-O therapy.

Patients on IV steroids may be switched to an equivalent dose of oral corticosteroids (e.g. prednisone) at start of tapering or earlier, once sustained clinical improvement is observed. Lower bioavailability of oral corticosteroids should be taken into account when switching to the equivalent dose of oral corticosteroids.

[figure not shown]
*Refer to NCI CTCAE v4 for term-specific grading criteria.

^If SJS/TEN is suspected, withhold I-O therapy and refer patient for specialized care for assessment and treatment. If SJS or TEN is diagnosed, permanently discontinue I-O therapy.

Updated 05-Jul-2016

Neurological Adverse Event Management Algorithm

Rule out non-inflammatory causes. If non-inflammatory cause, treat accordingly and continue I-O therapy.

Patients on IV steroids may be switched to an equivalent dose of oral corticosteroids (e.g. prednisone) at start of tapering or earlier, once sustained clinical improvement is observed. Lower bioavailability of oral corticosteroids should be taken into account when switching to the equivalent dose of oral corticosteroids.

Updated 05-Jul-2016

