5.6.5 NIVOLUMAB DOSE MODIFICATION

Adverse events (both non-serious and serious) associated with Nivolumab exposure may represent an immunologic etiology. These adverse events may occur shortly after the first dose or several months after the last dose of treatment. Nivolumab must be withheld for drug-related toxicities and severe or life-threatening AEs as per Appendix 2 below.

Nivolumab administration should be delayed for the following:

- Any Grade ≥ 2 non-skin, drug-related adverse event, with the following exceptions:
 - Grade 2 drug-related fatigue or laboratory abnormalities do not require a treatment delay
- Any Grade 3 skin, drug-related adverse event
- Any Grade 3 drug-related laboratory abnormality, with the following exceptions:
 - Grade 3 amylase or lipase abnormalities that are not associated with symptoms or clinical manifestations of pancreatitis do not require a dose delay.
 - If a subject has a baseline AST, ALT, or total bilirubin that is within normal limits, delay dosing for drug-related Grade ≥ 2 toxicity
 - If a subject has baseline AST, ALT, or total bilirubin within the Grade 1 toxicity range, delay dosing for drug-related Grade ≥ 3 toxicity
- Any adverse event, laboratory abnormality, or intercurrent illness, which, in the judgment of the investigator, warrants delaying the dose of study medication

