5.6.5.3 CRITERIA TO RESUME NIVOLUMAB

Subjects may resume treatment with study drug when the drug-related AE(s) resolve to Grade ≤ 1 or baseline value, with the following exceptions:

- Subjects may resume treatment in the presence of Grade 2 fatigue.
- Subjects who have not experienced a Grade 3 drug-related skin AE may resume treatment in the presence of Grade 2 skin toxicity.
- Subjects with baseline Grade 1 AST/ALT or total bilirubin who require dose delays for reasons other than a 2-grade shift in AST/ALT or total bilirubin may resume treatment in the presence of Grade 2 AST/ALT OR total bilirubin.
- Subjects with combined Grade 2 AST/ALT AND total bilirubin values meeting discontinuation parameters should have treatment permanently discontinued
- Drug-related pulmonary toxicity, diarrhea, or colitis, must have resolved to baseline before treatment is resumed.
- Drug-related endocrinopathies adequately controlled with only physiologic hormone replacement may resume treatment.

If the criteria to resume treatment are met, the subject should restart treatment at the next scheduled time-point per protocol. However, if the treatment is delayed past the next scheduled time-point per protocol, the next scheduled time-point will be delayed until dosing resumes. For example, if a dose is missed for 5 weeks, a subject can re-start immediately but if dosing is delayed 3 weeks, a subject will need to wait until the next scheduled dose at 4 weeks.

Treatment may be delayed for up to a maximum of 8 weeks from the last dose; if treatment is delayed > 8 weeks, the subject must be permanently discontinued from study therapy, except as

specified in Section 5.6.7.5. Please see also Appendix 2 (Management Algorithms) for guidance on appropriate management and follow-up of adverse events.

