5.6.5.4 DOSE DISCONTINUATION OF NIVOLUMAB

Treatment should be permanently discontinued for the following:

- Any Grade 2 drug-related uveitis or eye pain or blurred vision that does not respond to topical therapy and does not improve to Grade 1 severity within the re-treatment period OR requires systemic treatment.
- Any Grade 3 non-skin, drug-related adverse event lasting > 7 days, with the following exceptions for drug-related laboratory abnormalities, uveitis, pneumonitis, bronchospasm, neurologic toxicity, hypersensitivity reactions, and infusion reactions:
 - Grade 3 drug-related uveitis, pneumonitis, bronchospasm, neurologic toxicity, hypersensitivity reaction, or infusion reaction of any duration requires discontinuation.
 - Grade 3 drug-related laboratory abnormalities do not require treatment discontinuation except:
 - Grade 3 drug-related thrombocytopenia > 7 days or associated with bleeding requires discontinuation
 - Any drug-related liver function test (LFT) abnormality that meets the following criteria require discontinuation:
 - AST or ALT > 8 x ULN
 - Total bilirubin > 5 x ULN
 - Concurrent AST or ALT > 3 x ULN and total bilirubin > 2 x ULN
- Any Grade 4 drug-related adverse event or laboratory abnormality, except for the following events which do not require discontinuation:
 - Isolated Grade 4 amylase or lipase abnormalities that are not associated with symptoms or clinical manifestations of pancreatitis and decrease to < Grade 4 within 1 week of onset.
 - Isolated Grade 4 electrolyte imbalances/abnormalities that are not associated with clinical sequelae and are corrected with supplementation/appropriate management within 72 hours of their onset.
- Any dosing delay lasting > 8 weeks with the following exceptions:
 - Dosing delays to allow for prolonged steroid tapers to manage drug-related adverse events are allowed. Prior to re-initiating treatment in a subject with a dosing delay lasting > 8 weeks, the PI must be consulted. Tumor assessments should continue as per protocol even if dosing is delayed.
 - Dosing delays > 8 weeks that occur for non-drug-related reasons may be allowed if approved by the PI. Prior to re-initiating treatment in a subject with a dosing delay lasting > 8 weeks, the PI must be consulted. Tumor assessments should continue as per protocol even if dosing is delayed.

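### The hepatic footnote in Appendix 2 permits delaying nivolumab at some liver values for which Section 5.6.5.4 requires permanent discontinuation, and no sentence says which text governs

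*Combined protocol and SAP*

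**What the plan says.** Section 5.6.5.4 sets the permanent stopping rules. For liver tests it states: "Any drug-related liver function test (LFT) abnormality that meets the following criteria require discontinuation". Three criteria follow, and any one is enough: AST or ALT above 8 x ULN; total bilirubin above 5 x ULN; or "Concurrent AST or ALT > 3 x ULN and total bilirubin > 2 x ULN". They are listed as exceptions to a more lenient rule: "Grade 3 drug-related laboratory abnormalities do not require treatment discontinuation except".

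The hepatic algorithm in Section 11.2 (Appendix 2) has an asterisked footnote: "I-O therapy may be delayed rather than discontinued if AST/ALT ≤ 8 x ULN or T.bili ≤ 5 x ULN". As available, it makes no exception for AST/ALT and bilirubin raised together.

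Section 5.6.5.3, on resuming treatment, has one bullet on the combined pattern: "Subjects with combined Grade 2 AST/ALT AND total bilirubin values meeting discontinuation parameters should have treatment permanently discontinued". Its general rule is "Subjects may resume treatment with study drug when the drug-related AE(s) resolve to Grade ≤ 1 or baseline value". It then refers to the appendix: "Please see also Appendix 2 (Management Algorithms) for guidance on appropriate management and follow-up of adverse events". Section 5.6.5.1 describes the algorithms as recommended. None of these sections gives an order of precedence between 5.6.5.4 and Appendix 2.

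**The concern.** Both texts address the same decision, whether to delay or to stop for good, and they do not give the same answer. The footnote carries over two of the three liver limits and omits the concurrent one.

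The omitted criterion matters because 3 x ULN for AST/ALT and 2 x ULN for bilirubin are the two laboratory thresholds in the protocol's definition of potential drug-induced liver injury (Section 8.5). That definition also requires no initial cholestasis and no other apparent cause. A site working from the hepatic algorithm alone could delay a patient whom Section 5.6.5.4 says to stop, and later re-dose under the general resumption rule. Consultation with the principal investigator is required only when a delay exceeds 8 weeks (Sections 5.6.5.4 and 7.4.5), so a shorter delay would not trigger it.

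**Working it through.** The plan gives no numerical result to reproduce. The check compares the two rules case by case.

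**Inputs.** Let A = AST or ALT and B = total bilirubin, both as multiples of ULN, for a drug-related abnormality.

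- Stop, from the three liver criteria of Section 5.6.5.4: A > 8, or B > 5, or (A > 3 and B > 2).
- Delay permitted, Appendix 2 footnote, narrower reading ('or' means the limit on whichever test is abnormal, so both limits must hold): A ≤ 8 and B ≤ 5.
- Delay permitted, literal reading of 'or': A ≤ 8 or B ≤ 5.

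**Narrower reading.** If A ≤ 8 and B ≤ 5, the first two stopping criteria cannot be met. Only the concurrent criterion can put a patient in both sets, so the conflict is exactly 3 < A ≤ 8 with 2 < B ≤ 5.

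**Literal reading.** That region remains, and two more are added: A > 8 with B ≤ 5, and A ≤ 8 with B > 5. Only when A > 8 and B > 5 together does the footnote give no permission to delay.

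| A | B | 5.6.5.4 liver criteria | Footnote, narrower | Footnote, literal |
|---|---|---|---|---|
| 8 | 2 | none met | delay permitted | delay permitted |
| 3 | 5 | none met | delay permitted | delay permitted |
| 3.5 | 2.5 | stop (concurrent) | delay permitted: conflict | delay permitted: conflict |
| 5.5 | 3.5 | stop (concurrent) | delay permitted: conflict | delay permitted: conflict |
| 8 | 5 | stop (concurrent) | delay permitted: conflict | delay permitted: conflict |
| 8.5 | 1 | stop (A > 8) | no permission | delay permitted: conflict |
| 3 | 5.5 | stop (B > 5) | no permission | delay permitted: conflict |
| 8.5 | 5.5 | stop (both limits) | no permission | no permission |

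'No permission' means only that the footnote does not offer delay. What the chart itself instructs in those cases cannot be seen.

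**Does Section 5.6.5.3 close the gap?** In part. Its bullet on combined elevation stops patients with Grade 2 values that meet the discontinuation parameters. The liver criteria in 5.6.5.4 apply to any drug-related abnormality and sit as exceptions to the Grade 3 laboratory rule, so they also reach values above Grade 2. The resumption bullet, as worded, does not. For those values Section 5.6.5.3 leaves only its general rule of recovery to Grade 1 or lower, or to baseline.

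**Does the reworded footnote work?** The proposed condition is A ≤ 8 and B ≤ 5 and not (A > 3 and B > 2). This is the logical negation of the stop set above, so no combination is both delayed and stopped, and none is left uncovered. It complements the three liver criteria only, not the other stopping rules in 5.6.5.4.

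**The case against.** The strongest reply is that precedence is clear enough. Section 5.6.5.4 is the section on discontinuation, its wording is mandatory, and it lists its own exceptions, which do not include the footnote. The footnote only permits delay, the algorithms are recommended, and Section 5.6.5.3 cites them as guidance. An investigator who follows 5.6.5.4 breaches nothing visible in the appendix. This stands, and it is why the point is minor. It remains an inference that each site must draw for itself.

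The second reply is that the footnote qualifies a chart that is not available. The asterisk may mark a single grade, and a box in the chart may deal with combined elevation. This also stands: either would shrink the conflict.

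The third is that other safeguards exist. Section 5.6.5.3 catches combined Grade 2 values before resumption, and a stop at Grade 2 gives no reason to resume after something worse. Cases meeting the full definition in Section 8.5 must be reported as SAEs, within 24 hours under Section 8.7. These safeguards lower the risk, but SAE reporting sets no dosing rule.

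Two stronger readings are tempting and are not supported. A reader might infer that Appendix 2 overrides the body because Section 5.6.5 says "Nivolumab must be withheld for drug-related toxicities and severe or life-threatening AEs as per Appendix 2 below". That sentence makes the appendix binding for withholding drug; it gives no licence to re-dose a patient whom 5.6.5.4 stops. A reader might also infer that many patients would be affected. The documents give no distribution of liver values, so the conflict can be stated as a range of values but not as a proportion of patients.

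**Conclusion.** The inconsistency is real and minor. Within whatever grade the asterisk marks, the footnote permits delay where Section 5.6.5.4 requires discontinuation for drug-related AST/ALT above 3 and up to 8 x ULN with bilirubin above 2 and up to 5 x ULN. That range is in conflict on either reading of 'or'. The wider conflict, where just one of the two upper limits is exceeded, depends on taking 'or' literally.

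The conclusion assumes that the unseen chart contains no instruction on combined elevation that removes the conflict. Harm would require a site to rely on the footnote over 5.6.5.4 and, for combined Grade 2 values, over 5.6.5.3 as well. The issue is one of patient safety and consistent dosing. It does not touch the DFS analysis, the sample size or the error rates.

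**What to change.** Add one sentence to Section 5.6.5: *The liver discontinuation criteria in 5.6.5.4 govern over Appendix 2.* This works whatever the chart shows and leaves the algorithm text shared with the Investigator Brochure untouched.

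Optionally, also correct the footnote so that delay is allowed only with *AST/ALT ≤ 8 x ULN and T.bili ≤ 5 x ULN, and not concurrent AST/ALT > 3 x ULN with T.bili > 2 x ULN*. If the appendix has to match the Investigator Brochure, the sentence in 5.6.5 is enough.

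The cost is one sentence, or one sentence and one footnote, with no added patients, procedures or analyses.
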